## Hypotheses

Researchers' primary hypothesis is that participants randomized to the *popular online content SSI (The Blu Surfer Program)* will have greater reductions in distress between baseline and 8-week follow-up than those randomized to the *researcher-created SSI (the ABC Project)*.

As secondary hypotheses, researchers predict greater improvements in loneliness, general self-efficacy, hopelessness, meaning and purpose in life, and adaptive actions and thoughts in the *popular online content SSI* condition relative to the *researcher-created SSI*. Researchers also predict that participants randomized to the *popular online content SSI* will report greater reductions in distress than those randomized to the *online help-seeking as usual* condition.

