### *Exploratory hypotheses:*

1. Demographics and baseline mental health characteristics predict one's willingness to choose a certain kind of content.
2. The kinds of content one chooses predict change in distress between baseline and 8-week follow-up.
3. Participants add more pieces of content to their guide when provided an annotated library to choose from VS when they have to seek out their own content without a library.
4. Participants are more satisfied with their mental health resource guides after completing it when they choose content from an annotated library than when they choose it themselves.
5. Participants are more likely to view their mental health resource guide after 8 weeks when they choose content from a curated library than when they select it all on their own.
6. Younger participants will experience a greater reduction in distress after the popular

online content interventions than older participants at 8 weeks.

7. The annotated library condition (*blu surfer*) is more likely to lead to an insight experience than online help-seeking as usual.
8. Having an insight experience during an intervention is associated with greater improvement in distress at 8 weeks.
9. Higher baseline general self-efficacy is associated with greater improvement in distress at 8 weeks.
10. Engagement with the SSI predicts greater improvement in distress at 8 weeks.

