#### *Additional analyses testing exploratory hypotheses*

1. To test if demographic and baseline mental health characteristics predict one's willingness to choose a certain kind of content, researchers will conduct a separate multiple logistic regression for each kind of content one can choose in the content selection portion of the *blu surfer* program. Researchers define a "kind" of content as a topic (eg, emotional support, motivation, personal experience) or format (eg, video, image, article, activity). As demographic predictors, researchers will include age, gender, ethnicity, country, education level, employment status, socio-economic status, and having received professional mental health support in the past. As baseline mental health predictors, researchers will include distress, self-efficacy, hopelessness, meaning and purpose in life, adaptive actions and thought, and loneliness.
2. To test if the kinds of content one chooses predict change in distress over 8 weeks, researchers will conduct an MLM regression with each kind (defined as in the above analysis) as a binary predictor, study timepoint as another predictor, and the interaction between selected kind and timepoint as predictors, as well as a participant identifier as a random intercept.
3. To test how many pieces of content one adds when they pull content from an annotated library vs when they find it independently online, researchers will conduct a t-test of numbers of content added to one's guide across the "blu surfer" and "online help seeking as usual" conditions.

4. To test if participants are more satisfied in the *blu surfer* condition than the *online help seeking as usual* condition, researchers will conduct a t-test comparing mean satisfaction across those conditions.
5. To test if participants are more likely to view their mental health resource guide when they choose content from a curated library than when they select it all on their own, researchers will conduct a t-test comparing the mean number of times participants viewed their guide across the *blu surfer* and *online help-seeking as usual* conditions at 8 weeks after creating the guide.
6. To evaluate how age moderates change in distress over 8 weeks among participants completing popular online content interventions, researchers will conduct a mixed effects model with distress as the outcome, age, timepoint, and their interaction as predictors, and a participant identifier as a random intercept.

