7. To compare the frequency of insight experiences across the *blu-surfer* and *online help-seeking as usual* conditions, researchers will conduct a Chi-squared test.
8. To test how having an insight experience moderates the intervention's impact on change in distress over 8 weeks, researchers will run a mixed effects model with distress as the outcome, insight experience, measurement time point, and their interaction as predictors, and a participant identifier nested within experimental condition as a random intercept.
9. To test how baseline self-efficacy moderates the impact of the intervention on change in distress over 8 weeks, researchers will run a mixed effects model with distress as the outcome, baseline self-efficacy, measurement time point, and their interaction as predictors, and a participant identifier nested within experimental condition as a random intercept.
10. Researchers will test how engagement predicts improvement in distress at 8 weeks in two ways. First, researchers will run a mixed effects model with distress as the outcome, number of resources viewed from the list at week 8, measurement time point, and their interaction as predictors, and a participant identifier nested within experimental condition as a random intercept. Second, researchers will run a mixed effects model with distress as the outcome, number of pieces of content added to one's list, measurement time point, and their interaction as predictors, and a participant identifier

nested within experimental condition as a random intercept. These analyses will be limited to participants in the two popular online content conditions.

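### Study 2's two engagement models (exploratory item 10) omit condition × time, so an arm difference in change can be read as an engagement effect

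*Combined protocol and SAP*

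**What the plan says.** Study 2, additional analyses testing exploratory hypotheses, item 10, sets out two mixed models for distress. The first uses "number of resources viewed from the list at week 8, measurement time point, and their interaction as predictors"; the second uses "number of pieces of content added to one's list, measurement time point, and their interaction as predictors". In both, the random intercept is for participant nested within condition, and there is no fixed condition or condition × time term. On the sample, the item adds: "These analyses will be limited to participants in the two popular online content conditions". Those are two randomised arms, Blu Surfer and online help-seeking as usual. The Study 2 main model, by contrast, does contain time × condition.

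Elsewhere the plan predicts that these same two arms differ:
- **Change in distress.** The secondary hypotheses say Blu Surfer participants "will report greater reductions in distress than those randomized to the" help-seeking arm.
- **Content added.** Exploratory hypothesis 3: "Participants add more pieces of content to their guide when provided an annotated library to choose from". Exploratory analysis 3 is a t-test of "numbers of content added to one's guide across the" two arms.
- **Guide viewing.** Exploratory hypothesis 5: "Participants are more likely to view their mental health resource guide after 8 weeks when they choose content from a curated library". Exploratory analysis 5 is a t-test "comparing the mean number of times participants viewed their guide across the" two arms.

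Four other models pool arms, use a predictor that arises after randomisation, and also lack condition × time: Study 1 exploratory analyses 1 (insight) and 3 (characters typed), Study 2 item 8 (insight) and Study 3 item 5 (insight).

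**The concern.** A random intercept for condition lets one arm sit higher or lower overall. It does not let one arm improve faster. If Blu Surfer users both add or view more content and improve more, the pooled engagement × time slope will favour an engagement effect even when, inside each arm, engagement has nothing to do with change. The plan's own hypotheses supply both ingredients, in the direction that favours the hypothesis under test.

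What is at stake is the reading of an exploratory result. An arm difference could be reported as showing that adding or viewing more content goes with improvement. No primary or secondary conclusion is affected.

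**Working it through.** **Inputs.** The model terms and predicted arm differences come from the sections cited above. The 5% level comes from the Study 2 section on missing data handling and is taken as two-sided. The documents give no sample size, SD, correlation or effect size, so there is no planned figure to reproduce, and every such value below is an assumption.

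**1. Does nesting in condition help?** On one simulated data set, the engagement × (week 8 vs baseline) slope was 0.0450 (t = 0.717) with a participant intercept alone and the same with participant nested in condition. On a second data set it was -0.0380 as planned, -0.0380 with an arm level term, and -0.0040 with arm × time. Only the last addition changes the estimate.

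**2. Size of the between-arm part in item 10.** Take two equal arms, a within-arm engagement SD of 1 and no within-arm association. Let dE be the arm gap in engagement and dC the arm gap in 8-week change, both in SDs. The pooled covariance of engagement and change is dE·dC/4, and the pooled variance of engagement is 1 + dE²/4. The absolute slope is therefore

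0.25·dE·dC / (1 + 0.25·dE²)

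- dE 0.5, dC 0.3: 0.0375 / 1.0625 = 0.035
- dE 0.8, dC 0.4: 0.08 / 1.16 = 0.069

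The sign is negative (a larger fall in distress) when Blu Surfer is ahead on both.

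**3. Rejection rates, item 10.** Simulation used 4,000 trials per scenario, complete data, three visits with time as a factor, half of the week 8 change reached by week 4, correlation 0.7 and 100–200 per arm:

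| Gap in engagement | Gap in change | Rejection as planned |
|---|---|---|
| 0.2 SD | 0.1–0.2 SD | 5–6% |
| 0.5 SD | 0.3 SD | 11–15% |
| 0.8 SD | 0.4 SD | 28–48% |
| Counts, mean 2 vs 2.5 | 0.1 SD | 5% |
| Counts, mean 2 vs 4 | 0.3 SD | 11–15% |
| Gap in only one of the two | | 5–6% |

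Counts were negative binomial with dispersion 0.8. A separate simulation with correlation 0.6 (3,000 runs per cell) gave 9.4%, 13.0% and 19.3% at 100, 200 and 400 per arm for gaps of 0.5 and 0.3 SD. For the same gaps at 100–200 per arm, a normal approximation gives 8–11% at correlation 0.5 and 12–20% at 0.8.

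**4. The other four models.** With three equal arms and no within-arm association, the large-sample slope on insight is the between-arm covariance of insight and change, divided by p(1 - p), where p is the overall insight rate. For Study 2, assume changes of 0 / 0 / -0.3 SD for help-seeking / ABC / Blu Surfer, with insight at 20% / ABC rate / 40%:
- ABC 20%: -0.0133 / 0.1956 = -0.068; rejection 10–16%
- ABC 40%: -0.0067 / 0.2222 = -0.030; 6–7%
- ABC 60%: 0; 5–6%
- ABC 80%: 0.0067 / 0.2489 = +0.027, sign reversed; 6–7%

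The plan predicts that Blu Surfer exceeds help-seeking on insight but says nothing about ABC. Study 3 gives the same figures with the control in place of ABC and Overcoming Loneliness at 20%, provided neither of those two arms changes.

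For Study 1 characters typed, assume changes of 0 / -0.2 / -0.4 SD for control / SSI / 3-week. No engagement gap gives 5–6%. The 3-week arm 0.5 SD higher gives 12–17%. Control and 3-week both 0.5 SD higher gives 5–6%. The 3-week arm 0.5 SD lower gives 12–17% in the opposite direction.

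**5. With condition × time added**, rejection is 4–6% in every scenario.

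**The case against.** The strongest reply is that this is a choice of estimand. Hypothesis 10 says only that engagement predicts improvement, and a pooled slope answers that. The plan never states a null of no association within arms, so the slope is spurious only against a question it did not pose. This stands in part: a significant pooled result is not wrong as a description of the pooled sample. But the arm difference in change already has its own test. Study 3 states its engagement hypotheses separately for each SSI, and its content-choice analysis is limited to one arm. The within-arm reading is the natural one, and the pooled slope cannot be told apart from it.

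Other points on that side:
- **Arm gaps are reported elsewhere.** A reader would see the t-tests and the main model. This limits misreading but does not separate the two parts.
- **Guide views versus resources viewed.** Hypothesis 5 concerns the guide, item 10 resources from the list. The difference is slight, because Table 3 lists a single viewing measure.
- **Magnitudes are assumed.** True. The low end is plausible, since Study 2 Materials cites a similar self-study condition that did as well as a video on knowledge. Nothing in the documents supports gaps as large as 0.8 and 0.4 SD.
- **The other four models.** Their bias may be nil or reversed, so the case there is consistency. Study 1 item 3 is somewhat stronger: no arm hypothesis on characters is stated, but the 3-week arm has three sessions of prompts and is predicted to improve most.

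**Conclusion.** The concern holds as a minor one. All six models omit condition × time, and nesting in condition does not make up for it. In item 10 the plan's own hypotheses predict both arm gaps needed for the between-arm part to appear, in the favourable direction. Its size is unknown: negligible if either gap is small, and about -0.035 SD per SD with 11–15% rejection at gaps of 0.5 and 0.3 SD. That rests on 100–200 per arm, correlation 0.7, complete data and no within-arm association. For the other four models the plan fixes neither size nor sign. The omission is certain; how much it matters depends on arm gaps that the documents do not give.

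**What to change.** In item 10 first, and in the other four models for consistency, replace the condition grouping factor with fixed condition and condition × time, for example `lmer(distress ~ time*engagement + time*condition + (1|study_id))`, with loneliness as the outcome in Studies 1 and 3. Report the results as within-arm associations. Engagement and insight are not randomised, and week 8 viewing is recorded at the same visit as the outcome, so within-arm confounding remains. If the pooled association is also wanted, show it beside the adjusted one and label it as including arm differences.

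The baseline self-efficacy models can stay pooled, because randomisation makes a baseline predictor independent of arm. Separately, Study 2 items 8–9 and Study 3 items 5–6 speak of moderating the intervention's impact but contain no predictor × condition × time term. They should speak of association with change, as their hypotheses do.

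Cost: a formula edit in six exploratory models, a wording edit in four items, and no new data. In one mixed-model check at 150 per arm with a 0.5 SD engagement gap, the standard error of the engagement × time term rose from 0.0439 to 0.0459 (ratio 1.046, about 5%).

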### Tables describing measures

**Table 3.** Full list of primary, secondary, and screening variables collected during the study, including when during the trial they were assessed.

Measure (Primary, Secondary, Other)	Baseline	Post- Intervention	4-week follow-up	8-week follow-up
Depression Anxiety and Stress Scale – 9 item total score (primary)	X		X	X
3-item UCLA Loneliness Scale (secondary)	X		X	X
Short form of the General Self-Efficacy Scale (secondary)	X	X	X	X
Beck Hopelessness Scale – 4-item (secondary)	X	X	X	X
Frequency of actions and thoughts scale (secondary)	X		X	X
PROMIS Meaning and Purpose in Life – 4-item (secondary)	X		X	X
Program Feedback Scale (secondary)		X		
Credibility and Expectancy Questionnaire (secondary)		X		
Insight experience (secondary)		X		
Star rating (secondary)		X		
Number of times one viewed a resource from one's list of popular online content (secondary)			X	X
Patient Health Questionnaire – 4-item (screening)	X			

**Table 4.** Measures organized by dimension

Dimension	Application to project	Study Measurement(s)
Effectiveness	Improvements in symptoms and functioning	Primary: DASS-9 (depression, anxiety, and stress; used in this study as a proxy for psychological distress) Secondary: ULS-3, GSE-6 (general self-efficacy), Beck Hopelessness Scale, Meaning and Purpose in Life measure, FATS (frequency of adaptive behaviors and thoughts related to therapeutic change)
Engagement	Satisfaction with intervention and aspects of experience	PFS (satisfaction with SSI), CEQ (intervention credibility and expectations of impact), insight experience, star rating (program quality), number of times viewed resource
Screening	Inclusion in main analyses and reimbursement	PHQ-4 (depression/anxiety, used as proxy for psychological distress)

### **Study 3: Trial of a popular online content-based single-session intervention for loneliness**

#### **Procedure**

Researchers will use social media and the University of California, Irvine Social Ecology subject pool to recruit a diverse online sample of English-speaking participants aged 16+ with access to the internet and a computer, tablet, or smartphone. To advertise the study on social media, researchers will use both paid and unpaid posts on several social media platforms, potentially including Instagram, Reddit, Tumblr, Twitter, Facebook, LinkedIn, 4chan, and others. Researchers may also use the online subject recruitment platform Researchmatch. Finally, researchers may collaborate with Healthy Gamer, a web-based mental wellness company, to share information about the study with Healthy Gamer's online community Discord and Subreddit, reaching 20,000-25,000 people.

To ensure a sufficient number of participants for analysis who are experiencing loneliness, if one's score on the ULS-3 meets the study criterion for "struggling with loneliness", one will be offered reimbursement of a \$10 Amazon gift card that researchers will email them once they complete the final follow-up 8 weeks later, provided they completed all 4 evaluations (pre-test, post-test, 4-week, and 8-week). Researchers will consider an individual to be struggling with loneliness if their score on the ULS-3 is 6 or higher and they answer affirmatively that their loneliness is causing them distress (Steptoe et al., 2013).

Participants who do not meet the criteria for "struggling with loneliness" will still have the opportunity to complete the study without compensation. They will also be allowed to access the two non-control conditions (see Materials for more information) directly if they prefer to not participate in the study. Participants are only allowed to complete the study once.

Those who participate through the UC Irvine subject pool will receive 1 hour of participation credit for completing the first part of the study. If UC Irvine subject pool participants meet criteria for struggling with distress, they will also be offered a \$10 gift card for completing all parts of the study.

#### *Study process*

After participants complete the loneliness screen, read the study information, and agree to participate, they complete baseline self-report measures of mental health outcomes and demographics. Next, they complete an intervention (see materials for intervention information).

After completing the intervention, participants are offered access to a browser and PDF version of the intervention they completed to keep and/or share with others. They are also referred to other online resources for people struggling with mental health. Next, they complete a few brief measures of hope, agency, meaning in life, and engagement with the intervention platform. 4 and 8 weeks later, they will receive links via email to complete follow-up measures of mental health outcomes and engagement. At the end of the 8-week follow-up, participants are given access to all three conditions in PDF and browser forms. The entire study will be conducted using the secure online experience management platform Qualtrics and several anti-fraud / bot measures will be included in the survey.

## Materials

The *Overcoming Loneliness* program is a 25-minute SSI for loneliness that the researchers created by adapting Käll et al.'s 9-week therapist-supported iCBT for loneliness (Käll, Shafran, et al., 2020). Käll et al.'s iCBT focuses on person-level psychological factors contributing to the maintenance of loneliness; it aims to help challenge maladaptive thoughts and encourage social behaviors (more information on Käll et al.'s iCBT available at [www.iterapi.se/sites/solus/](http://www.iterapi.se/sites/solus/)) (Käll, Shafran, et al., 2020). It is text-based and self-guided. Following Käll et al.'s iCBT, the loneliness intervention includes content relating to understanding loneliness, setting goals and values, testing thoughts and behaviors, making plans, gaining social confidence, and overcoming barriers. Broadly, the intervention uses behavioral activation, cognitive restructuring, and behavioral experimentation strategies. The loneliness interventions also pull some content from Jessica Schleider et al.'s single-session mental health interventions (<http://www.schleiderlab.org>) and take inspiration from their interventions' aesthetics and their strategy of using Qualtrics to develop and provide the intervention.

The *Lonely Blu Surfer* program is a 25-minute SSI that the research team developed centered on popular online content relevant to mental health. In the SSI, each user is first asked to select the kinds of support they would like to view. Next, the user is asked to explore a library of annotated popular online content (filtered by the kinds of support they chose) and to select the content they find personally valuable. The user is asked to explore a library of annotated popular online content and to select the content they find personally valuable. Researchers crowdsourced this library by asking people from online

communities and an undergraduate psychology course lecture to contribute one piece of popular online content that they believed could help someone struggling with loneliness. Researchers also pulled some content relevant to loneliness from the original *Blu Surfer* program's library, which included content for psychological distress and other mental health challenges. Finally, the SSI provides the user a list of the content they selected to keep and draw from, build on, or share with friends.

In the control condition, participants complete a supportive therapy SSI, called "The Sharing Feelings Project", of roughly equivalent length and style to the loneliness SSI (J. L. Schleider & Weisz, 2019). Previous work showed this control to be slightly less efficacious in improving mental health outcomes in adolescents than a growth mindset SSI and a behavioral activation SSI (J. L. Schleider et al., 2022; J. Schleider & Weisz, 2018). The supportive therapy SSI "encourages participants to express emotions to close others", but "does not teach specific skills". (J. L. Schleider et al., 2022; J. Schleider & Weisz, 2018). Researchers borrowed the supportive therapy SSI from the Lab from Scalable Mental health and slightly modified it to make it more applicable to both teens and adults, as it was originally designed for teens only (link to SSI: <https://osf.tvio/u4axs/>, license: <https://creativecommons.org/licenses/by-nc-sa/4.0/>) (J. L. Schleider & Weisz, 2019).

